AE adverse event; BP blood pressure; C Cycle; CTCAE v5.0 Common Terminology Criteria for Adverse Events version 5.0; ECOG Eastern Cooperative Oncology Group; eCRF electronic case report form; GI gastrointestinal; HBV hepatitis B virus; HCV hepatitis C virus; HIV human immunodeficiency virus; ICF informed consent form; LFT liver function test; PD progressive disease; Q28days every 28 days; Q4W every 4 weeks; RECIST 1.1 Response Evaluation Criteria in Solid Tumors version 1.1; SAE serious adverse event; SoA schedule of activities; SoC standard of care; T3 triiodothyronine; T4 thyroxine; TSH thyroid-stimulating hormone; WHO World Health Organization.

Table 3 Schedule of assessments for patients who previously received treatment with durvalumab monotherapy or durvalumab in combination with any other approved or investigational anticancer agents, and are not eligible for any future treatment (Cohort 3)

Evaluation	Baseline/ Enrollment	Time since the last dose of study drug ^a			Long-term follow-up
		Day (±3 days)	Day (±7 days)		
		30	60	90	
Informed consent					
Informed consent ^b	X				
Eligibility criteria ^b	X				
Study procedures					
Vital signs ^c		X	X	X	
Physical examination ^d		X			
Concomitant medications		X	X	X	
Subsequent anticancer therapy ^e	X	X	X	X	X
Laboratory safety assessments					
Clinical chemistry		X	X	X	
Hematology		X	X	X	
TSH (reflex free T3 or free T4) ^f		X	X	X	
Pregnancy test ^g		X			
Monitoring					
AE/SAE assessment ^h		X	X	X	
Survival status ⁱ					X
Tumor Assessments					
Tumor assessment ^j	Assessment performed according to the Investigator's standard practice until withdrawal of consent, progression or death.				

- a. Follow-up visits are performed based on the duration since the last dose of study drug in either the parent clinical study or current study (whichever most recently administered the study drug). Patients who are more than 90 days beyond the last dose of study drug will not undergo follow-up for AEs/SAEs, vital signs, concomitant medications or laboratory safety assessments; these patients will be followed for survival.
- b. Informed consent of study procedures may be obtained prior to enrollment, if necessary. Patients in Cohort 3 will sign the follow-up ICF, and must meet the eligibility criteria detailed in Sections 5.1 and 5.2.
- c. Vital signs include temperature, respiratory rate, BP, and pulse. Body weight is measured along with vital signs.

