8.3.2 Time period and frequency for collecting AE and SAE information

AEs and SAEs will be collected from the time of the patient signing the ICF until the follow-up period is completed (90 days after the last dose of durvalumab). If an event that starts post the defined safety follow-up period noted above is considered to be due to a late onset toxicity to study drug, then it should be reported as an AE or SAE as applicable. Collection and reporting of AEs and SAEs after the final DCO is described in Section [8.3.14](#).

All SAEs will be recorded and reported to the Sponsor or designee within 24 hours, as indicated in [Appendix A](#). The Investigator will submit any updated SAE data to the Sponsor within 24 hours of it being available.

Investigators are not obligated to actively seek AE or SAE in former study patients. However, if the Investigator learns of any SAE, including a death, at any time after a patient's last visit and he/she considers the event to be reasonably related to the study treatment or study participation, the Investigator should notify the Sponsor.

The method of recording, evaluating, and assessing causality of AE and SAE and the procedures for completing and transmitting SAE reports are provided in [Appendix A](#).

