1 STUDY DETAILS

1.1 Study objectives

The study objectives will be assessed among 3 cohorts defined according to treatment status, these cohorts are described in Section 1.2.

The objectives of this study as well as corresponding endpoints are as follows:

Table 1. Study objectives and endpoints

Primary objective	Endpoints/Variables:
To monitor long term safety of durvalumab (all cohorts)	
 • All SAEs • Non-serious AEs that lead to dose modification, drug discontinuation, or withdrawal from the study • All Grade 3 and Grade 4 AEs • Grade 2 AEs that affect vital organs (eg, heart, liver) • Immune-mediated AEs • Laboratory findings qualifying as an SAE/AE (endpoints defined above) up until 90 days after the last dose of durvalumab in all patients
Secondary Objectives:	Endpoints/Variables:
To assess the efficacy of durvalumab in terms of ORR and DOR in patients who undergo retreatment with durvalumab (Cohort 2 only)	
ORR: Number (%) of patients with a confirmed response of CR or PR.
 
DOR: Time from first documented CR or PR to time of first documented disease progression or death in the absence of disease progression

To assess the OS of patients (all cohorts)	
OS: Time from date of randomization/date of first dose ^a in the parent clinical study until the date of death by any cause

AE adverse event; CR complete response; DOR duration of response; ORR Objective response rate; OS overall survival; PR partial response; SAE serious adverse event.

^a For randomized parent studies, the randomization date will be used in the calculation of OS. For single-arm parent studies, the date of first dose will be used in the calculation of OS.

[figure not shown]

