2.1.3 Safety Analysis Set (SAS)

The SAS will consist of patients who received at least 1 dose of durvalumab on this study or enrolled on this study within 90 days of the last dose of durvalumab or durvalumab combination on the respective parent clinical study. The primary objective analysis will be assessed in the SAS.

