4 OTHER ASSESSMENTS

In addition to primary and secondary variables that will be collected under this study, other key information will be collected using either directly into Electronic Data Capture (EDC) system or transferred from clinical parent studies (Table 2).

Table 2. Parent study assessments

Study variables	Data source

 • Parent study protocol number, study e-CODE 	EDC entry

 • Vital signs (weight, temperature, blood pressure, pulse rate, respiratory rate) 	

 • Date and last dose of durvalumab and durvalumab combination treatment administration 	

 • Ongoing safety events at the end of parent study 	

Study variables	Data source

 • Ongoing concomitant medications at the end of the parent study • Subsequent anticancer therapy 	

 • Patient identification or linkage key, including connection to the Interactive Voice/Web Response System (IxRS) and EDC and transfer of old enrolment code (E-code) • Demographics: date of birth 	New IxRS system

 • Date of randomization from parent study (for randomized parent studies) • Date of first administration of durvalumab and durvalumab combination treatment (for non-randomized parent studies). • Height 	Transfer of data from clinical parent study (SDTM data)

 • Contact information: (patient, caregiver, physician) as allowed by regulation for each country 	Patient contact module

In addition to parent study assessments, the following data will be collected and described:

- Disposition of Subjects, assessed at study termination, under “disposition (DS)” eCRF module. The following information will be collected:
 - Discontinuation date
 - Subject’s status at discontinuation: Death, Lost to follow-up, Screen failure, Withdrawal by subject, Withdrawal by parent/guardian, Development of study-specific withdrawal criteria (to be specified), Other (to be specified), Adverse Event, and Pregnancy
- Patient demographic and Other Baseline Characteristics assessed at baseline visit:
 - Age
 - Sex
 - Race
 - Ethnicity
 - Country
- **[Only for Cohort 1 and Cohort 2]** Exposure to durvalumab assessed under “Exposure - durvalumab (EX)” eCRF module. The following information will be collected:
 - Start date and time
 - End date and times

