5 ANALYSIS METHODS

5.1 General principles

The below mentioned general principles will be followed throughout the study:

- Descriptive statistics will be used for all variables, as appropriate. Continuous variables will be summarized by the number of observations, mean, standard deviation(Sd), median, upper and lower quartiles minimum, and maximum. Categorical variables will be summarized by frequency counts and percentages for each category.
- Unless otherwise stated, percentages will be calculated out of the population total for the corresponding analysis set.
- For continuous data, the mean and median will be rounded to 1 additional decimal place compared to the original data. The Sd will be rounded to 2 additional decimal places compared to the original data. Minimum and maximum will be displayed with the same accuracy as the original data.
- For categorical data, percentages will be rounded to 1 decimal place.
- There are no statistical methods that will be employed to test a specific hypothesis.
- SAS® version 9.4 or later will be used for all analyses.

For efficacy endpoints (only considered for Cohort 2), the last observed measurement prior to retreatment will be considered the baseline measurement.

For safety endpoints (where all cohorts are considered) the last observation before the first dose of study treatment will be considered the baseline measurement. For assessments on the day of first dose/randomization date where time is not captured, a nominal pre-dose indicator will serve as sufficient evidence that the assessment occurred prior to first dose. Assessments

on the day of the first dose where neither time nor a nominal pre-dose indicator are captured will be considered prior to the first dose if such procedures are required by the protocol to be conducted before the first dose.

In all summaries change from baseline variables will be calculated as the post-treatment value minus the value at baseline. The percentage change from baseline will be calculated as $(\text{post-baseline value} - \text{baseline value}) / \text{baseline value} \times 100$.

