5.2.5 Safety

Safety data will be summarized according to the treatment received for the SAS (all patients who received at least 1 dose of durvalumab either as continuation of study treatment or retreatment in this study, and inclusive of patients who received the last dose of durvalumab or durvalumab combination from the parent clinical study within 90 days of enrollment [all cohorts]). AEs, vital signs, dose at time of AE, and laboratory safety assessments (clinical chemistry, hematology and thyroid stimulating hormone [reflex free triiodothyronine or free thyroxine]) will be listed individually by patient.

The number of patients experiencing each AE will be summarized by study cohort and CTCAE grade (v5.0). Each patient will be represented with the maximum reported CTCAE grade for each system organ class / preferred term. Number (%) of patients with AEs, will be sorted by international System Organ Classes (SOC) order and alphabetical PT and then maximum grade. Event rate per 100 patient-years will also be calculated for each AE.

Individual laboratory measurements and vital signs data will be presented in listing format.

For laboratory measurements, the following data will be listed:

- Subject identifier and cohort
- Age/sex/race
- Analysis visit
- Category of lab test
- Lab test examination name

- Result/finding
- Units
- Reference range indicator

For vital signs, the following data will be listed:

- Subject identifier and cohort
- Vital signs test name
- Analysis visit
- Result
- Unit
- Result clinically significant (yes/no)
- Reference ranges (upper and lower limits).

For vital signs, the following reference ranges and units will be used:

- For Diastolic blood pressure: Range = 40-110, Unit = mmHg
- For Heart rate/Pulse: Range = 50-120, Unit = beats/min
- For Respiratory rate: Range = 12-35, Unit = breaths/min
- For Systolic blood pressure: Range = 60-160, Unit = mmHg
- For Temperature: Range = 35-39, Unit = °C / Range = 95-102.3, Unit = °F
- For Weight: Range = 30-140, Unit = Kg / Range = 66-308, Unit = LB
- Oxygen saturation: 95-100%, unit-free.

Note: Based on an “as needed” request from parent clinical studies, safety data from WAVE may be combined with parent study data in order to update safety summaries.

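### For safety-set patients not dosed in WAVE, the AE n (%) ignores delayed entry and understates 0-90 day post-dose incidence by an amount that depends on enrollment lag and AE duration

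*SAP*

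**What the plan says.** SAP 2.1.3 admits to the safety set anyone dosed in WAVE, and also anyone who "enrolled on this study within 90 days of the last dose of durvalumab or durvalumab combination on the respective parent clinical study". The second route brings in Cohort 3 patients and Cohort 2 patients who are never retreated.

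Protocol 8.3.2 sets the collection window: "AEs and SAEs will be collected from the time of the patient signing the ICF until the follow-up period is completed", which means 90 days after the last dose. Protocol 1.1, Table 3 note a, closes it at the far end: "Patients who are more than 90 days beyond the last dose of study drug will not undergo follow-up for AEs/SAEs". Protocol 9.3.3.1 bases the AE summary tables on events up to 90 days after durvalumab is discontinued. The endpoint list in SAP 1.1 uses the phrase "up until 90 days after the last dose of durvalumab in all patients", attached to laboratory findings.

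SAP 5.2.5 tabulates patients with each AE as number and percent, by cohort and maximum CTCAE grade. SAP 5.1 gives the default denominator: "percentages will be calculated out of the population total for the corresponding analysis set". No exception is made for this table. SAP 5.2.5 adds that "Event rate per 100 patient-years will also be calculated for each AE", without saying when a patient's time starts or stops.

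The parent-study safety information listed in SAP 4, Table 2 is "Ongoing safety events at the end of parent study". SAP 5.2.5 also allows WAVE and parent safety data to be combined, on request.

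**The concern.** A patient not dosed in WAVE who consents on day u after the last parent dose is observed for 90 - u days. Consent on day 85 gives 5 days of observation but adds one whole patient to the denominator. Neither document has a rule for this delayed entry.

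The AE percentage for these patients therefore mixes windows of 0 to 90 days, and the part that is missing is always the earliest part of the post-dose period. That part matters here. Exclusion criterion 3 in Protocol 5.2 keeps patients who stopped durvalumab permanently for toxicity out of Cohorts 1 and 2, but it does not apply to Cohort 3.

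Because the table is by cohort, undosed Cohort 2 patients also share a column with retreated ones, whose observation is quite different. A reader who takes the figure as post-dose incidence, for a primary safety objective, would read it too low for reasons of transfer timing.

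**Working it through.** The plan states no AE incidence, lag distribution or AE duration, so there is no figure of its own to reproduce. The window (90 days), the start of collection (consent) and the denominator (whole set) come from the sections above. The risk, lag, hazard shape and duration below are assumptions.

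**Step 1. No carry-over.** Let R be the true 90-day risk and take a constant hazard h = -ln(1 - R)/90 per day. A patient consenting on day u shows an event with probability 1 - exp(-h(90 - u)). With u uniform on 0-90, the mean observed window is 45 days and the average of this expression is 1 - R/(-ln(1 - R)).

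- R = 10%: 1 - 0.10/0.1054 = 5.1%, a loss of 49%
- R = 30%: 1 - 0.30/0.3567 = 15.9%, a loss of 47%
- R = 50%: 1 - 0.50/0.6931 = 27.9%, a loss of 44%

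**Step 2. Other lags, R = 30%** (h = 0.3567/90 = 0.00396).

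| Consent day | Table shows | Loss |
|---|---|---|
| all at day 7 | 1 - exp(-0.00396 × 83) = 28.0% | 7% |
| uniform 0-30 | 25.7% | 14% |
| uniform 0-45 | 23.4% | 22% |
| uniform 0-90 | 15.9% | 47% |
| uniform 30-90 | 11.0% | 63% |
| all at day 80 | 3.9% | 87% |

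**Step 3. Hazard shape, R = 30%, uniform 0-90.** If the hazard halves after day 45, the table shows 13.3%, a loss of 56%. With a Weibull cumulative hazard, the loss is 64% for shape 0.5 (front-loaded) and 37% for shape 1.5 (rising).

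**Step 4. Credit for events still ongoing at consent, R = 30%, uniform 0-90.** Take AE durations as exponential with mean m days, events as recurrent, and every event ongoing at consent as carried over and counted. The expected number of counted events given u is h[(90 - u) + m(1 - exp(-u/m))], and the probability of at least one is 1 minus the exponential of minus that number. Averaging over u:

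| Mean duration m | Table shows | Loss |
|---|---|---|
| 14 days | 19.8% | 34% |
| 30 days | 22.6% | 25% |
| 60 days | 25.3% | 16% |
| 90 days | 26.6% | 11% |

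If no event ever resolved, nothing would be missed. Step 1 is the opposite limit, in which no gap event is counted.

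**Step 5. The patient-year rate, R = 10%.** Here h = 0.1054/90 = 0.001171 per day, or 0.001171 × 365.25 × 100 = 42.8 events per 100 patient-years. Person-time from consent to day 90 recovers 42.8 under a constant hazard. Crediting every patient with a full 90 days, with uniform 0-90 day consent, halves it to 21.4. The SAP does not say which applies.

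**The case against.** The strongest reply is that the plan already softens the problem in three ways.

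- **Ongoing events are carried over.** Protocol 8.2.1 lists ongoing safety events at the end of the parent study, including SAEs and AESIs, and says the transfer list may be modified. It is tempting to infer that all events before consent are lost. The documents do not support that: only events that both start and resolve in the gap are certain to be missing from the WAVE table, and the parent study may have recorded them. This stands, and it reduces the size (Step 4). Even so, the SAP does not say whether carried-over events count in the Cohort 3 table. Its on-treatment window in 3.2.1 runs from a start dose that is not defined for a patient with no WAVE dose.
- **A rate per 100 patient-years is planned.** With person-time from consent, it removes the delayed-entry bias under a constant hazard. But person-time is undefined, SAP 5.2.8 summarizes exposure only for Cohort 1 and retreated Cohort 2, and a correct rate leaves the n (%) as it was.
- **Pooling with parent data is allowed.** It is optional and on request, so it does not complete WAVE's own table.

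A reader might also infer that Cohort 3 will look safer than Cohort 1. The plan tests no hypothesis, and Cohort 1 is treated until progression, so its crude percentage already covers a different and usually longer period. The two columns were never comparable as 90-day risks. Nor do the documents call the Cohort 3 percentage a 90-day incidence. The point is about how that percentage will be read against the 90-day window the plan sets for safety.

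**Conclusion.** The concern holds in a limited form. Followed as written, the plan gives Cohort 3 and undosed Cohort 2 AE percentages that are too low as measures of 0-90 day post-dose incidence. The direction follows from the documents, provided that some AEs start and resolve before consent. The size does not follow from them, because it depends on enrollment lag and AE duration.

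For a true 30% risk and a constant hazard, the loss is about 47% with uniform 0-90 day consent and no carry-over, 11-34% once events ongoing at consent are counted, and about 7% with prompt consent at day 7. A reader might take the first figure and say that incidence is understated by about half. That requires a mean lag near 45 days, a roughly constant hazard, a low-to-moderate risk and no credit for carry-over, none of which is stated. Nor is the loss always material: prompt rollover keeps it below 10%.

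The SAP should be changed, because the remedy is cheap and the actual size will be known only once the lags are tabulated.

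**What to change.** In SAP 5.2.5:

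1. Report safety-set patients not dosed in WAVE separately from dosed patients, including within Cohort 2.
2. Define person-time for the per-100-patient-year rate in these patients as consent to day 90 after the last dose, or earlier end of follow-up.
3. Show cumulative incidence on the time-since-last-dose scale with entry at the consent day (left truncation), in place of a crude percentage read as 90-day incidence.
4. Report the median observed window by cohort.
5. State how parent-study events carried over as ongoing are counted.

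Where a parent study holds AEs with onset between the last dose and consent, add them to the parent SDTM transfer that SAP 4, Table 2 already plans for randomization date, first-dose date and height. Flag them by source and CTCAE version.

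Items 1 to 5 use dates and events already collected and need no new visits or patients, only a little more analysis work. The AE transfer costs more: parent AE windows and CTCAE versions are not known from these documents, and parent events re-entered in WAVE as ongoing must be reconciled. Left-truncated estimates will also be imprecise near day 0, where few patients are at risk.

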2.2 Violations and deviations

The following general categories will be considered important protocol deviations; such protocol deviations will be reviewed and categorized by the medical team, and the Epidemiology team based on data from the Clinical Trial Management System (CTMS) data, and finally confirmed with the site management team. Subject and site level protocol deviations are collected from the CTMS. Subject-level protocol deviations will be listed and discussed in the clinical study report (CSR) as appropriate:

- **Deviation 1:** Patients who deviate from key entry criteria per the Clinical Study Protocol (CSP). Key entry criteria are the following (please refer to the CSP for more details):
 - Patient received durvalumab monotherapy and/or durvalumab containing combination in an AstraZeneca/MedImmune-sponsored parent clinical study that is approved for enrollment into this study.
 - Patients who received durvalumab in combination with any other approved or investigational anticancer agents in the parent clinical study must have completed or discontinued all other anticancer therapy (beyond durvalumab regimen).
[Additional inclusion criteria for patients entering Cohort 1]
 - Currently receiving durvalumab monotherapy (this includes patients enrolled in durvalumab combinations who have completed or discontinued all other anticancer therapy combined with durvalumab in the parent clinical study, and are now receiving durvalumab monotherapy), and is currently benefiting from treatment with durvalumab therapy, as determined by the Investigator.
[Additional inclusion criteria for patients entering Cohort 1 and Cohort 2]
 - Adequate organ function (see detailed definition in the CSP)
 - Evidence of postmenopausal status or negative urinary or serum pregnancy test for female premenopausal patients.
 - World Health Organization / Eastern Cooperative Oncology Group (ECOG) performance status (PS) of ≤ 2 at enrolment
[Additional inclusion criteria for retreatment patients in Cohort 2]
 - Received durvalumab in a parent clinical study that is approved to enroll into this study
 - Completed the defined treatment duration with durvalumab monotherapy or durvalumab combination therapy in the parent clinical study (see more details in the CSP)
 - At least 1 lesion that can be accurately measured at baseline as ≥ 10 mm in the longest diameter (except lymph nodes which must have a short axis ≥ 15 mm) with computed tomography or magnetic resonance imaging), and that is suitable for accurate repeated measurements as per RECIST v1.1 guidelines.

In addition, patients are considered as with deviation if any of the exclusion criteria are met:

- Involvement in the planning and/or conduct of the study (applies to both AstraZeneca staff and/or staff at the study site).
- [Additional exclusion criteria for Cohort 1 and Cohort 2]
- Currently receiving treatment in another interventional clinical study other than a parent clinical study, or received treatment during the follow-up period before retreatment (Cohort 2 only).
 - Experienced an immune-mediated or non-immune-mediated (hematologic and non-hematologic) toxicity that led to permanent discontinuation of durvalumab in the parent clinical study.
 - With any unresolved toxicity National Cancer Institute (NCI) Common Terminology Criteria for Adverse Events (CTCAE) Grade ≥ 2 from previous anticancer therapy with the exception of alopecia, vitiligo, and the laboratory values defined in the inclusion criteria
 - Prior treatment with immunotherapy other than durvalumab, or any other approved or investigational anticancer agents other than MedImmune/AstraZeneca's investigational immunotherapy molecules administered in the parent clinical study
 - Active or prior documented autoimmune or inflammatory disorders (including inflammatory bowel disease [eg, colitis or Crohn's disease], diverticulitis [with the exception of diverticulosis], systemic lupus erythematosus, Sarcoidosis syndrome, or Wegener syndrome [granulomatosis with polyangiitis, Graves' disease, rheumatoid arthritis, hypophysitis, uveitis, etc]). The following are exceptions to this criterion:
 - (a) Patients with vitiligo or alopecia.
 - (b) Patients with hypothyroidism (eg, following Hashimoto syndrome) stable on hormone replacement.
 - (c) Any chronic skin condition that does not require systemic therapy.
 - (d) Patients without active disease in the last 5 years may be included but only after consultation with the Study Physician.
 - (e) Patients with celiac disease controlled by diet alone.
 - History of allogenic organ transplantation
 - Uncontrolled intercurrent illness, including but not limited to, ongoing or active infection, symptomatic congestive heart failure, uncontrolled hypertension, unstable angina pectoris, uncontrolled cardiac arrhythmia, active interstitial lung disease, serious chronic Gastro Intestinal (GI) conditions associated with diarrhea, or psychiatric illness/social situations that would limit compliance with study requirement, substantially increase risk of incurring AEs or compromise the ability of the patient to give written informed consent.

- Documented active infection including tuberculosis (clinical evaluation that includes clinical history, physical examination(PE) and radiographic findings, and tuberculosis testing in line with local practice), hepatitis B virus (HBV) (known positive HBV surface antigen [HbsAg] result), hepatitis C virus (HCV), or human immunodeficiency virus (HIV) (positive HIV 1/2 antibodies). Patients with a past or resolved HBV infection (defined as the presence of hepatitis B core antibody and absence of HbsAg) are eligible. Patients positive for HCV antibody are eligible only if polymerase chain reaction is negative for HCV RNA. Prior HIV and HBV/HCV testing from the parent clinical study is acceptable documentation and patients will not need to undergo an additional testing prior to Cohort 1 enrollment in this study. For Cohort 2 patients, prior HIV testing from the parent clinical study is acceptable documentation and patients will not need to undergo an additional test prior to retreatment. However, patients will require retesting for HbsAg and HCV within the 28-day window prior to retreatment
- Receipt of live attenuated vaccine within 30 days prior to the first dose of study drug in the present study. Note: Patients, if enrolled, should not receive live vaccine while receiving study drug and up to 90 days after the last dose of study drug
- Female patients who are pregnant or breastfeeding, or male or female patients of reproductive potential who are not willing to employ effective birth control from screening to 90 days after the last dose of durvalumab monotherapy or 180 days after the last dose of durvalumab + tremelimumab combination.
- Diagnosis of a new primary malignancy since enrollment into the parent clinical study, with the exception of adequately treated non-melanomatous skin cancer and carcinoma in situ with No Evidence of Disease (NED).
- Must not have required the use of additional immunosuppression other than corticosteroids for the management of an AE >Grade 1, have not experienced recurrence of an AE if re-challenged, and not currently require maintenance doses of >10 mg prednisone or equivalent per day
- Known allergy or hypersensitivity to any of the study drugs or any of the study drug excipients
- **Deviation 2:** Baseline RECIST scan date is greater than 28 days before the date of starting Cycle 1 of retreatment for Cohort 2, during the WAVE study period.
- **Deviation 3:** No baseline RECIST 1.1 assessment on or before the date of starting Cycle 1 of retreatment (Cohort 2), during the WAVE study period.
- **Deviation 4:** Received prohibited concomitant medications (including other anticancer agents). Please refer to the CSP Section 6.4 for those medications that are detailed as being ‘excluded’ from permitted use during the study. This will be used as a guiding principle for the medical data reviewer of all medications prior to database lock.

All the violations and deviations considered only come from WAVE without taking into account data from parent studies. The important subject-level protocol deviations will be listed and summarized by treatment group (study cohort) in the main part of the CSR. All

participants with important protocol deviations will be listed by center, as an appendix. Site level protocol deviations are collected from the CTMS. The important site level protocol deviations will be listed, as an appendix of the CSR.

